### General PK Parameter Rules

- Actual sampling times will be used in the final analyses of individual PK parameters, except for non-bolus pre-dose sampling times which will be set to zero.
- Cmax and tmax will be reported from observed values. If Cmax occurs at more than one timepoint, tmax will be assigned to the first occurrence of Cmax.
- AUC parameters will be calculated using a combination of the linear and logarithmic trapezoidal methods (linear-log trapezoidal rule). The linear trapezoidal method will be applied up to tmax and then the logarithmic trapezoidal method will be used after tmax. The minimum requirement for the calculation of AUC will be the inclusion of at least three consecutive plasma concentrations above the LLOQ, with at least one of these concentrations following Cmax. AUC(0-∞) values where the percentage of the total area extrapolated is more than 20% will be flagged. Any AUC(0-∞) value excluded from summary statistics will be noted in the footnote of the summary table.
- Half-life associated with the terminal rate constant ( $\lambda_z$ ) in non-compartmental analysis (t1/2) will be calculated, when appropriate, based on the apparent terminal log-linear portion of the concentration-time curve. The start of the terminal elimination phase for each participant will be defined by visual inspection and generally will be the first point

at which there is no systematic deviation from the log-linear decline in plasma concentrations. Half-life will only be calculated when a reliable estimate for this parameter can be obtained comprising of at least 3 data points. If  $t_{1/2}$  is estimated over a time window of less than 2 half-lives, the values will be flagged in the data listings. Any  $t_{1/2}$  value excluded from summary statistics will be documented in the footnote of the summary table.

- A uniform weighting scheme will be used in the regression analysis of the terminal log-linear portion of the concentration-time curve.
- The parameters based on observed  $C_{last}$  will be reported.

### Individual PK Parameter Rules

- Only quantifiable concentrations will be used to calculate PK parameters with the exception of special handling of certain concentrations reported below the lower limit of quantitation (BQL). Plasma concentrations reported as BQL will be set to a value of zero when all of the following conditions are met:
  - The compound is non-endogenous.
  - The samples are from the initial dose period for a participant or from a subsequent dose period following a suitable wash-out period.
  - Predose concentrations  $> 5\% C_{max}$  will be flagged with exclusions to be noted.
  - The time points occur before the first quantifiable concentration.
- All other BQL concentrations that do not meet the above criteria will be set to missing.
- Also, where two or more consecutive concentrations are BQL towards the end of a profile, the profile will be deemed to have terminated and therefore any further quantifiable concentrations will be set to missing for the calculation of the PK parameters unless it is considered to be a true characteristic of the profile of the drug.

### Individual Concentration vs. Time Profiles

- Individual concentrations will be plotted utilizing actual sampling times.
- The terminal point selections will be indicated on a semi-logarithmic plot.

### Average Concentration vs. Time Profiles

- The average concentration profiles will be graphed using scheduled (nominal) sampling times.
- The average concentration profiles will be graphed using arithmetic average concentrations.

- The pre-dose average concentration for single-dose data from non-endogenous compounds will be set to zero. Otherwise, only quantifiable concentrations will be used to calculate average concentrations.
- Concentrations at a sampling time exceeding the sampling time window specified in the protocol, or  $\pm 10\%$ , will be excluded from the average concentration profiles.
- Concentrations excluded from the mean calculation will be documented in the CSR.
- A concentration average will be plotted for a given sampling time only if 2/3 of the individual data at the time point have quantifiable measurements that are within the sampling time window specified in the protocol or  $\pm 10\%$ . An average concentration estimated with less than 2/3 but more than 3 data points may be displayed on the mean concentration plot if determined to be appropriate and will be documented within the CSR.

### **Treatment of Outliers during Pharmacokinetic Analysis**

Application of this procedure to all PK analyses is not a requirement. Rather, this procedure provides justification for exclusion of data when scientifically appropriate. This procedure describes the methodology for identifying an individual value as an outlier for potential exclusion, but does not require that the value be excluded from analysis. The following methodology will not be used to exclude complete profiles from analysis.

#### Data within an Individual Profile

A value within an individual profile may be excluded from analysis if any of the following criteria are met:

- For PK profiles during multiple dosing, the concentration of the pre-dose sample exceeds all measured concentrations for that individual in the subsequent post-dose samples.
- For PK profiles during single dosing of non-endogenous compounds, the concentration in a pre-dose sample is quantifiable.
- For any questionable datum that does not satisfy the above criteria, the profile will be evaluated and results reported with and without the suspected datum.

#### Data between Individual Profiles

1. If  $n < 6$ , then the dataset is too small to conduct a reliable range test. Data will be analyzed with and without the atypical value, and both sets of results will be reported.
2. If  $n \geq 6$ , then an objective outlier test will be used to compare the atypical value to other values included in that calculation:
  - a. Transform all values in the calculation to the logarithmic domain.

- b. Find the most extreme value from the arithmetic mean of the log transformed values and exclude that value from the dataset.
- c. Calculate the lower and upper bounds of the range defined by the arithmetic mean  $\pm 3*SD$  of the remaining log-transformed values.
- d. If the extreme value is within the range of arithmetic mean  $\pm 3*SD$ , then it is not an outlier and will be retained in the dataset.
- e. If the extreme value is outside the range of arithmetic mean  $\pm 3*SD$ , then it is an outlier and will be excluded from analysis.

If the remaining dataset contains another atypical datum suspected to be an outlier and  $n \geq 6$  following the exclusion, then repeat step 2 above. This evaluation may be repeated as many times as necessary, excluding only one suspected outlier in each iteration, until all data remaining in the dataset fall within the range of arithmetic mean  $\pm 3*SD$  of the log-transformed values.

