### **9.3 Pharmacokinetic Assessment**

#### **9.3.1 Pharmacokinetic Analysis**

Noncompartmental methods applied with a validated software program (WinNonlin Phoenix v8.1 or later) to the plasma concentrations of LY573144 and its metabolite M8 will be used to determine the following PK parameters, when possible:

Parameter	Units	Definition
AUC(0-t last )	ng*h/mL	area under the concentration versus time curve from time zero to time t, where t is the last time point with a measurable concentration
AUC(0-∞)	ng*h/mL	area under the concentration versus time curve from time zero to infinity
%AUC(t last -∞)	%	percentage of AUC(0-∞) extrapolated
C max	ng/mL	maximum observed drug concentration
t max	h	time of maximum observed drug concentration
t 1/2	h	half-life associated with the terminal rate constant ( $\lambda_z$ ) in non-compartmental analysis
CL/F	L/h	apparent total body clearance of drug calculated after extra-vascular administration (not M8)
V z /F	L	apparent volume of distribution during the terminal phase after extra-vascular administration (not M8)
V ss /F	L	apparent volume of distribution at steady state after extra-vascular administration (not M8)

Additional PK parameters may be calculated, as appropriate. The software and version used for the final analyses will be specified in the CSR. Any exceptions or special handling of data will be clearly documented within the CSR.

Formatting of tables, figures and abbreviations will follow the Eli Lilly Global PK/PD/TS Tool: NON-COMPARTMENTAL PHARMACOKINETIC STYLE GUIDE. The version of the tool effective at the time of PK analysis will be followed.

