#### Reporting of Excluded Values

Individual values excluded as outliers will be documented in the CSR. Approval of the CSR will connote approval of the exclusion.

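### SAP 9.3.1: with six or more values, an optional 3-SD test removes a flagged value without a cause or a full-data result, and the bioequivalence model is not stated to be exempt

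*SAP*

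**What the plan says.** The opening paragraph on outliers in SAP 9.3.1 makes the procedure optional. It is offered as a justification for exclusion where that is scientifically appropriate, and it "does not require that the value be excluded from analysis". It adds: "The following methodology will not be used to exclude complete profiles from analysis".

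Three situations are then treated differently:

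- **A questionable concentration within one profile:** "the profile will be evaluated and results reported with and without the suspected datum".
- **Between profiles, fewer than six values:** "Data will be analyzed with and without the atypical value, and both sets of results will be reported".
- **Between profiles, six or more values:** a test is used to "compare the atypical value to other values included in that calculation". The most extreme log value is set aside, and the mean ± 3 SD of the rest is computed. If the value falls outside that range, "then it is an outlier and will be excluded from analysis". The step may be repeated while at least six values remain.

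On reporting: "Individual values excluded as outliers will be documented in the CSR. Approval of the CSR will connote approval of the exclusion". The general text of 9.3.1 also says: "Any exceptions or special handling of data will be clearly documented within the CSR".

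SAP 9.3.2 puts all valid PK data into the mixed model for Cmax, AUC(0-tlast) and AUC(0-∞). It does not define valid and does not mention the outlier test.

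**The concern.** With 36 planned completers, each treatment has far more than six values, so the third branch governs this trial. That branch has three gaps.

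1. **No cause and no paired result.** Distance alone meets the exclusion step. The paired reporting demanded in the other two branches is absent.
2. **Open scope.** Elsewhere the SAP says what an exclusion applies to: summary statistics for AUC(0-∞) and half-life (General PK Parameter Rules), or summary statistics and statistical analysis for the vomiting rule (SAP 8). The 3-SD step says only analysis. It can be read to cover the Cmax and AUC values in the bioequivalence model, or not to.
3. **Late approval.** Exclusions are documented, so they are not hidden. But no full-data 90% CI has to stand beside the reduced one, and approval comes only with the study report, in an open-label trial.

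The wording also conflicts. The opening paragraph leaves exclusion optional, while the step makes it automatic. The bar on excluding complete profiles most naturally prevents removal of every parameter of a profile; it does not address removing one Cmax and keeping that profile's AUC.

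At stake is the primary conclusion. A genuine low Cmax on the new formulation is evidence that a bioequivalence test should count.

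**Working it through.** **Inputs from the documents.** 36 completers, Cmax CV 24.1% (taken as within-participant), true ratio 1.05, limits 0.80–1.25, 90% CI, 25% dropout (Protocol 9.2, SAP 7); 6 sequences × 3 periods (Table LAIA.1); tmax 1.8 h and half-life 5.7 h (Protocol 2.2).

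**The plan's sample size reproduces.** Exact TOST power with 2n−4 residual df is 89.4% at n = 32, 91.0% at 34 and 92.4% at 36. The next multiple of 6 after 34 is 36, and 36/0.75 = 48.

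**One low OD-without-water Cmax.**

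- Within-participant log SD = √ln(1 + 0.241²) = 0.238.
- Observations: 108. Fitted terms: 36 participants + 2 periods + 2 treatments = 40. Residual df = 68; leverage = 40/108 = 0.370.
- With clean complete data, the 90% half-width is 1.668 × 0.238 × √(2/36) = 0.093, so the ratio must be at least 0.80 × e^0.093 = 0.878.
- A value low by a log amount d moves the log ratio down by d/36 and adds 0.63 d² to the expected residual sum of squares. The ratio apart from that value must be at least 0.80 × exp(half-width + d/36).
- After removing that cell, the variance factor is 2/36 + (1/36)²/0.63 = 0.0568 with 67 df. The half-width is 0.094 and the required ratio 0.879.

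| Low value, as share of expected | d | d/36 | Half-width | Required ratio, all data | After removal |
|---|---|---|---|---|---|
| one-half | 0.693 | 0.019 | 0.097 | 0.899 | 0.879 |
| one-third | 1.099 | 0.031 | 0.102 | 0.914 | 0.879 |
| one-fifth | 1.609 | 0.045 | 0.111 | 0.935 | 0.879 |

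**Would the test flag such a value?** The lower bound is exp(−3 × total log SD), with total variance ln(1 + CVb²) + 0.0565. At an assumed between-participant CV (CVb) of 20%, 30% and 40%, it is 0.40, 0.32 and 0.26 of the geometric mean. One-half is seldom flagged. With one low value among 36, one-third is flagged in 71%, 49% and 31% of sets.

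**What a Cmax-only fall implies.** In a one-compartment model with first-order absorption and AUC kept, Cmax is proportional to exp(−ke × tmax). Dividing Cmax by k moves tmax to 1.8 + 5.7 × ln k/ln 2: 7.5 h, 10.8 h and 15.0 h for k = 2, 3 and 5. These are markedly prolonged absorptions.

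**Clean data.** On normal log data, the rule removes at least one genuine value in about 20% of sets of 36, and in 43–48% of trials across the three treatments. A flag alone is weak evidence of error. At a true ratio of 0.80, the Cmax type I error is 5.0–5.4% with all data, 5.4–6.3% after the rule, and 5.8–6.6% if either result may be used.

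**Illustration with assumed contamination.** 6,000 runs per scenario, SAP model, rule applied by treatment to Cmax only. Assumed and not in the documents: overall true Cmax ratio 0.80, AUC ratio 1.00, 5% of OD-without-water doses low in Cmax only, between-participant CV 20–40%, Cmax–AUC correlation 0.7, the two AUCs treated as one. Cmax and AUC must both pass.

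| Low values | Pass rate, all data | Pass rate, after rule | Low values removed |
|---|---|---|---|
| one-half | 5% | 7–8% | 7–18% |
| one-third | 7% | 11–19% | 22–55% |
| one-fifth | 9% | 26–38% | 54–91% |

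Monte Carlo standard error is 0.3–0.6 points. For one-third with 2% or 10% of doses low (Cmax test alone), the rates are 6% against 8–10% and 8% against 16–29%. If Cmax and AUC fall together and only Cmax is removed, they are 4% against 4% (one-third) and 6% against 7–8% (one-fifth).

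**The case against.** The strongest reply has four parts.

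- **The opening paragraph governs.** Exclusion is only potential and needs scientific judgement, so the step is not a mechanical deletion rule. This stands as a reading, but no criteria for the judgement are given and the step itself is unconditional.
- **The difference at six values is deliberate.** The SAP says fewer than six are too few for a reliable range test, so a test replaces paired reporting above that. That explains the difference, but it gives no reason to omit the full-data interval from a primary comparison.
- **The rule may concern only noncompartmental summaries.** It sits in 9.3.1, the model is in 9.3.2, and where the SAP means to remove data from statistical analysis it says so. This reading is available. The SAP does not state it, and one sentence would settle it.
- **At the planning values a single low value changes nothing.** With a ratio of 1.05 apart from that value, the all-data 90% CI is about 0.92–1.13 (one-third) or 0.90–1.12 (one-fifth); at 0.95, the lower limits are 0.83 and 0.81. All pass. This stands: one value decides only if the ratio from the rest lies in 0.879–0.914 or 0.879–0.935.

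It is also true that doses are supervised with mouth checks (Protocol 6.4), vomiting has its own rule (SAP 8), all databased data are listed (SAP 9.1), and the SAP is to be signed before the first visit (SAP 3). These limit the risk, but none of them requires the full-data CI to be reported.

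**Conclusion.** The point holds. For the case that applies here, the SAP permits removal on distance alone, requires no companion full-data result, and leaves open whether the primary model is affected. Two analysts could follow it and reach different primary datasets.

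The harm is conditional. It needs the rule to be applied to model values, a genuine low OD-tablet Cmax with AUC largely kept, and a ratio near the lower limit. The single-value thresholds rest on the plan's inputs, with the CV read as within-participant. The contamination pass rates rest on assumed frequencies and sizes of low values and show direction and scale, not a forecast. The conclusion carries moderate confidence and is worth acting on because the correction is cheap.

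**What to change.** In SAP 9.3.1 and 9.3.2:

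- State that the 3-SD test may flag, but not remove, Cmax, AUC(0-tlast) or AUC(0-∞) values in the primary bioequivalence models.
- Allow exclusions only for pre-specified, documented causes, such as assay failure, a dosing error or the existing vomiting rule, settled before the treatment comparison is run.
- Extend the paired reporting to six or more values, with the outlier-excluded result as a sensitivity analysis.
- Reconcile the optional and automatic wording, and define valid data, complete profiles, and the calculations to which the test applies.

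The cost is SAP wording and one sensitivity run if a value is flagged. The sample size does not change. The downside is that a truly aberrant value without a documented cause stays in the primary model and can widen the CI; the sensitivity analysis would show how much.

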#### Reporting of Excluded Values

Individual values excluded as outliers will be documented in the CSR. Approval of the CSR will connote approval of the exclusion.

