#### Example SAS Code:

```
proc mixed data = xxx;
  by parameter;
  class treatment period sequence participant;
  model log_pk = treatment period sequence / cl residual;
  random participant(sequence);
  lsmeans treatment / cl pdiff alpha = 0.1;
  ods output lsmeans=lsmeans diffss=diffs;
run;
```

All valid PK data will be included, whether or not the participants completed all 3 periods.

Estimates of geometric least square (LS) mean ratios together with the corresponding 90% CIs will be derived for the comparisons of AUC (0- $\infty$ ), AUC(0- $t_{last}$ ), and  $C_{max}$  as follows:

- Primary endpoint: lasmiditan OD tablet without water (test) versus lasmiditan IR tablet
- Secondary endpoint: lasmiditan OD tablet with water (test) versus lasmiditan IR tablet.

The 2 lasmiditan formulations will be considered bioequivalent if the 90% CIs of the ratio of geometric LS means of AUC (0-∞), AUC(0-tlast), and Cmax falls completely within 0.80 to 1.25.

Values of tmax will be analyzed non-parametrically using the Wilcoxon signed rank test. Estimates of the median difference between test and reference formulations based on the observed medians, 90% CIs, and the p-value from the Wilcoxon test will be calculated.

Additional PK analyses may be conducted if deemed appropriate.

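### The only approval of excluded PK values is sign-off of the study report, and exclusion is discretionary, so the SAP permits an exclusion to be settled after the bioequivalence result is known

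*SAP*

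**What the plan says.** All the relevant rules are in SAP 9.3.1, with the model in 9.3.2.

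- **Status of the procedure** (Treatment of Outliers during Pharmacokinetic Analysis): "Application of this procedure to all PK analyses is not a requirement", and identifying an outlier "does not require that the value be excluded from analysis". One limit is set: "The following methodology will not be used to exclude complete profiles from analysis".
- **Within one concentration profile**: some values may be removed on stated criteria. For any other questionable concentration, the profile is evaluated and "results reported with and without the suspected datum".
- **Between profiles, fewer than 6 values**: "Data will be analyzed with and without the atypical value, and both sets of results will be reported".
- **Between profiles, 6 or more values**: a numeric test on the log scale. The most extreme value is set aside and compared with the mean ± 3 SD of the rest. Step 2d keeps it if it lies inside that range. Step 2e removes it if it lies outside. The test may be repeated.
- **Record and approval** (Reporting of Excluded Values): "Individual values excluded as outliers will be documented in the CSR", followed by "Approval of the CSR will connote approval of the exclusion".
- **The model** (SAP 9.3.2): "All valid PK data will be included, whether or not the participants completed all 3 periods". The word 'valid' is not defined.

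Protocol 6.3 describes an open-label study and names central randomization as the protection against bias. SAP section 3 and Protocol 9.4 both require the SAP to be final before the first participant visit.

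**The concern.** Bioequivalence is a pass/fail decision: the 90% confidence intervals for Cmax and both AUCs must lie within 0.80 to 1.25. The data entering that decision should be fixed before anyone sees the outcome. Here the only approval of an exclusion comes with the report that contains the intervals, and treatment is known throughout.

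Timing would matter little if removal were automatic. It is not. The introduction to the outlier procedure leaves removal to judgement, while step 2e reads as mandatory, and the numeric test starts only when somebody regards a value as atypical. The test limits which values can go. It does not settle whether a flagged value goes, or when that is decided.

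At stake is the 5% limit on a false bioequivalence claim. A sponsor able to see the result with and without a flagged value could keep the version that passes. That would also weaken the reason for finalizing the SAP before the first visit.

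**Working it through.** **Inputs from the documents** (Protocol 9.2, SAP 7): 36 completers, six sequences, three periods; Cmax CV 24.1%; true ratio 1.05 for power; limits 0.80 and 1.25; 5% two one-sided tests; 25% dropout.

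**Assumptions not in the documents**: the CV is within-participant; the between-participant log SD is 0.3 (range 0.2 to 0.4); residual shape and the share of aberrant values are as stated below.

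**1. The plan's own figure.** Log SD = √ln(1 + 0.241²) = 0.2376. SE of the log ratio = 0.2376 × √(2/36) = 0.0560. With 2 × 36 − 4 = 68 df, exact power is 92.4%. The smallest n for 90% is 33, and the next multiple of 6 is 36. Enrolment is 36/(1 − 0.25) = 48. Both figures reproduce, and neither depends on this point.

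**2. How often the choice arises.** The test sets aside one of 36 values and compares it with the mean ± 3 SD of the other 35. For normal data the equivalent t threshold is 3/√(1 + 1/35) = 2.958 on 34 df, with two-sided probability 0.0056. Expected flags per treatment are 36 × 0.0056 = 0.20. For IR and OD without water together, the chance of at least one flag is about 1 − exp(−0.40) = 33%. Simulation gives about 34% with normal residuals and 58% to 59% with t residuals on 3 df. Counting OD with water as well gives about 47% and 72%, but that treatment is not part of the primary comparison.

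**3. False bioequivalence at a true ratio of 1.25.** Each simulated trial has 36 participants in the 6×3 design. The 3-SD rule is applied to log Cmax by treatment. Participant fixed effects stand in for the mixed model, which is equivalent for complete data and approximate after exclusions. Choosing means that the trial passes if either version passes.

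| Residuals | Runs | All data | 3-SD rule always applied | Favourable result chosen | Chosen minus always |
|---|---|---|---|---|---|
| Normal | 8,000 | 5.2% | 5.6% | 5.9% | 0.3 |
| Normal | 40,000 | 5.3% | 5.5% | 5.9% | about 0.35 |
| t, 3 df | 8,000 | 5.5% | 6.2% | 7.3% | 1.1 |
| t, 3 df | 40,000 | 5.1% | 5.5% | 6.9% | 1.4 |

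The Monte Carlo SE of a single rate near 5% is √(0.05 × 0.95/8,000) = 0.24 points, or 0.11 points at 40,000 runs. The last column isolates the effect of late choice. The step from all data to the rule always applied belongs to the outlier criterion itself.

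**4. Sensitivity** (6,000 runs per cell, both margins, between-participant log SD 0.2 to 0.4). The favourable choice gives 5.2% to 6.1% for clean log-normal data, 6.2% to 7.2% if 1% of values are too low by a factor of 3, and 6.4% to 8.4% if 3% are. With no exclusions, the rate is 4.7% to 5.7% throughout. The excess over a fixed rule is about 0.3 to 0.5 points for clean data and about 0.6 to 1.65 points with contamination.

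**The case against.** The strongest reply is that the main case already has an objective rule. With about 36 values per treatment, the numeric test applies to Cmax and AUC, and steps 2d and 2e say what follows from it. Whole profiles are protected, every exclusion is documented, and the exclusion rules come ahead of the model in the SAP.

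Most of this stands, and it rules out three stronger readings:

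- *Exclusions will be decided at report approval.* The SAP says that they are documented and approved then. It does not say that they are made then.
- *Two competing results always exist, with no rule to choose between them.* Paired results are called for only for a questionable concentration within a profile and for fewer than 6 values. For Cmax and AUC at the planned size, the SAP does not ask for both.
- *Any inconvenient Cmax can be dropped once the result is seen.* Step 2d keeps a tested value that lies within 3 SD. Removing a questionable peak concentration would make the next-highest concentration the Cmax. It would not delete the participant's Cmax. An error rate computed on free deletion does not describe this SAP.

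The reply does not remove the conflict between step 2e and the introduction to the procedure, which says that removal is not required. Nor does it supply an approval step before the model is run. Documentation makes an exclusion visible, but it does not fix the decision in advance.

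**Conclusion.** The point holds as a gap in control. Report sign-off is the only approval of excluded PK values, removal is discretionary by one passage and mandatory by another, and nothing requires the decision to precede the bioequivalence model.

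The size is modest. At the 1.25 margin, choosing the favourable result gives about 5.9% with normal residuals and about 7% with heavy tails, against a nominal 5%. The part due to choice is about 0.3 to 1.4 points over a fixed 3-SD rule. These figures rest on the assumed between-participant SD and residual shapes. They also treat Cmax alone at its margin. Because both AUCs must pass too, the overall false-claim rate under the same choice cannot exceed the Cmax rate.

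The occasion for choice would not be rare, at about 34% to 59% of simulated trials, and the correction is cheap. It should be made, but the documents do not support a claim that the primary conclusion would be seriously compromised.

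**What to change.** Three changes to SAP 9.3.1:

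1. Replace the sentence that ties approval of an exclusion to approval of the CSR with: *All PK exclusions, with their cause, are listed and approved in a signed, dated record before the Section 9.3.2 model is run; the CSR reports that record.*
2. Reconcile the introduction to the outlier procedure with step 2e, so that it is fixed in advance whether a value failing the 3-SD test is removed.
3. Wherever results with and without a value are both produced, state in advance which one decides bioequivalence and label the other a sensitivity analysis.

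The cost is a few sentences and one dated memo. The drawback is that a genuine data error found after the model is run could be handled only as a labelled sensitivity analysis. The sample size is unaffected.
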